6.2.5 Subgroup analyses

A pre-specified subgroup analysis, comparing pain scores by type of analgesia (paravertebral block versus intercostal block versus both versus neither) will be performed. This will consist of adding analgesia*treatment interaction terms to the pain score model (see Figure F8).

6.2.6 Sensitivity analyses

A pre-specified sensitivity analysis excluding participants with benign disease will be performed for the primary outcome (see Table T21).

Sensitivity analyses of overall survival and disease-free survival will be performed, adjusting for patient's disease stage based on pathological findings (see Figure F11).

Note: these analyses of survival were not pre-specified in the protocol but added upon recommendation from the Data Monitoring and Safety Committee (DMSC).

6.2.7 Exploratory analyses

Two exploratory analyses of pain scores will be undertaken, the first is stated in the protocol, the second was requested by the DMSC.

1. Comparing pain scores in the first two days by incisions (VATS single port versus VATS with multiple port sites versus open surgery) (see Tables T22 and T23).
2. Comparing pain scores in the first two-days post-surgery and at follow-up by type of thoracotomy performed (anterior thoracotomy versus posterolateral thoracotomy versus VATS; muscle sparing versus no muscle sparing; and rib-resection versus no rib-resection) (see Figure F12 and Figure F13).

An exploratory analysis comparing length of stay by incisions (VATS single port versus VATS multiple port versus open surgery) will be performed (see Table T24). This analysis of length of stay was not pre-specified in the protocol but requested by the chief investigator before any comparative analyses were performed.

6.2.8 Missing data

In all tables missing data for continuous variables will be indicated by footnotes. For category variables missing data will be highlighted by use of observation counts. If the amount of missing data differs substantially between treatment groups potential reasons will be explored.

Missing predictors:

There will be no missing data for any of the randomisation factors (by design). All other potential predictors are baseline measurements of continuous longitudinal outcomes, and due to the joint modelling approach described previously the handling of missing values for such data is considered in the context of missing longitudinal data (see below).

Missing outcomes measured at one time point:

- If the proportion of missing data is less than 5% then complete case analysis will be performed (i.e. excluding cases with missing data).
- If the proportion of missing data is above 5% multiple imputation methods will be considered. A general imputation model that uses an iterative procedure to generate imputed values will be used to generate multiple complete data sets (e.g. using Stata's `mi impute`). The model of interest will be fitted to each of the complete data sets and effect estimates combined using Rubin's rules. If appropriate, methods such as predictive mean matching will be used in order to ensure that imputed values lie within specific ranges.

Missing longitudinal data:

- For continuous data measured at multiple time points preoperative values will be modelled jointly with those measured postoperatively, as described previously, thereby allowing all cases with at least one observation to be included. If the proportion of cases that do not have at least one observation is above 5% then multiple imputation methods will be considered (see above). If appropriate (the level of missingness is >20%) then any variables that are predictive of missingness will be identified, and if there is reason to suggest that an assumption of missing at random (MAR) given these variables is reasonable (especially likely if the variable was measured pre-operatively) then such variables will be adjusted for in the models of interest. These models can be shown to provide unbiased estimates of the treatment effect and moreover multiple imputation approaches would not be expected to recover any additional information.

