8. AMENDMENTS TO THE SAP

[figure not shown]
Previous version	Previous date	New version	New date	Brief summary of changes
1.0	04/07/2019	2.0	11/11/2019	
Addition of the outcome upstaging to pN1 at the request of the chief investigator.
 
Updating analysis models section to state risk ratios and risk differences will be presented instead of odds ratios for binary outcomes.
 
Addition to safety data section to state all events will be MedDRA coded and the difference in proportion of patients experiencing an event in each MedDRA system organ class group will be reported.
 
Update to adjustment in models section to remove adjustment for analgesia in pain score models as it was decided analgesia lay on the causal pathway and may therefore lead to biased estimates. Analgesia will be summarised by group instead.

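### The rule for more than 20% missing longitudinal data does not exclude covariates that allocation affects, yet calls the resulting treatment effect unbiased without limit

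*SAP*

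**What the plan says.** The rule is in SAP section 6.2.8, under missing longitudinal data. Section 6.2.2 lists physical function, the primary outcome, among the longitudinal outcomes, so the rule applies to it.

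- Trigger and scope: "If appropriate (the level of missingness is >20%) then any variables that are predictive of missingness will be identified".
- Condition for use: MAR given these variables must be judged reasonable. The SAP calls this "especially likely if the variable was measured pre-operatively".
- Action, and property claimed for it: "such variables will be adjusted for in the models of interest. These models can be shown to provide unbiased estimates of the treatment effect".
- Alternative set aside: "multiple imputation approaches would not be expected to recover any additional information".

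Three other places bear on the point. Section 3.5 puts the main analyses on an intention-to-treat basis. Sections 2.4 and 6.2.2 treat time to discharge and in-hospital adverse events as outcomes to be compared between arms. Section 8 records why adjustment for analgesia was taken out of the pain models: "it was decided analgesia lay on the causal pathway and may therefore lead to biased estimates".

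**The concern.** Two different questions are run together. Whether data are MAR given a variable decides whether that variable helps in handling the missing values. Whether it may be a covariate in the model that estimates the effect of allocation is a separate matter, and there the variable must not itself be changed by allocation. Section 6.2.8 asks only the first question.

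Saying that measurement before surgery makes a variable more likely to qualify implies that one measured later may qualify too. Complications and length of stay are natural candidates, and the trial itself compares both between arms. If one were affected by allocation and related to function, adding it would turn the primary estimate from the total effect of allocation into something closer to a direct effect. The unbiasedness claim would then be false for the effect that section 3.5 calls for.

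The remark on imputation fails in the same case. Imputation can use such a variable to predict missing scores without conditioning the treatment effect on it.

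**Working it through.** The SAP states no figure that could be reproduced here. The check is on the logic, with an illustration of size.

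**Does any text confine the rule to safe covariates?** There are two gates: the 20% trigger with its appropriateness proviso, and plausibility of MAR. Neither concerns the effect of allocation on the variable. Earlier in section 6.2.8, under missing predictors, the SAP says "All other potential predictors are baseline measurements of continuous longitudinal outcomes". That describes covariates already planned for the models and does not limit the later search for predictors of missingness.

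**Inputs.** From the SAP: target effect 0.25 SD with 90% power at two-sided 5% (section 3). Assumed, not in the SAP: a complication lowers function by 0.5 SD; the chance of a missing score is 15% without a complication and 40% with one; complication rates differ between arms as shown below.

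**Formulas.** Let p_V and p_O be the complication rates under VATS and open surgery, with total effect 0.25.

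- Adjusted for complications: 0.25 − 0.5 × (p_O − p_V).
- Observed cases, not adjusted: the adjusted value + 0.5 × (q_O − q_V), where q = 0.60p / [0.60p + 0.85(1 − p)] is the complication rate among those observed.
- Imputed by arm using complications, analysis model unchanged: the adjusted value + 0.5 × (p_O − p_V), which returns 0.25.

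**Worked case, 30% against 45%.**

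- q_V = 0.18 / 0.775 = 0.232 and q_O = 0.27 / 0.7375 = 0.366.
- Missing overall: 1 − (0.775 + 0.7375) / 2 = 24%.
- Adjusted: 0.25 − 0.5 × 0.15 = 0.175.
- Not adjusted: 0.175 + 0.5 × 0.134 = 0.242.

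| Complications, VATS vs open | Adjusted | Not adjusted | Imputed by arm |
|---|---|---|---|
| 30% vs 45% | 0.175 | 0.242 | 0.25 |
| 30% vs 40% (q 0.232, 0.320) | 0.200 | 0.244 | 0.25 |
| 35% vs 40% (q 0.275, 0.320) | 0.225 | 0.247 | 0.25 |
| 40% vs 40% | 0.25 | 0.25 | 0.25 |

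A simulation with the same inputs agreed: 0.17, 0.20 and 0.225 adjusted, 0.24 to 0.25 otherwise. In the last row allocation does not change the variable, and adjusting does no harm.

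**Second check, continuous post-operative variable.** In a simulation of 400,000 patients (outcome SD between 0.89 and 1.08), the total effect was 0.25, about 23% of scores were missing, and 0.05, 0.10 or 0.15 of the effect passed through the variable. Adjusting gave 0.198, 0.148 and 0.100. Using the variable only to impute gave 0.248, 0.250 and 0.250. Observed cases without it gave 0.245, 0.245 and 0.243. With a baseline predictor of missingness instead, adjusting gave 0.251 and not adjusting 0.270, so the SAP's claim is sound there.

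**Consequence for power.** With the standard error unchanged, 90% power at 0.25 SD means an expected z of 1.960 + 1.282 = 3.242. An expected estimate of 0.20 gives 3.242 × 0.8 − 1.960 = 0.633, or about 74% power.

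**The case against.** The strongest reply is that the SAP names no post-operative variable, leans towards pre-operative ones, and makes the step conditional. The section 8 entry shows that the team knows the danger of adjusting for a variable on the causal pathway, which makes a poor choice less likely. All of this stands. A reader might infer that the SAP plans to adjust for complications or length of stay, but it does not say so. The wording only fails to exclude it. For the same reason section 8 is at odds with the rule in its reasoning and is not a literal contradiction.

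Further limits also stand:

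- A reader might take the 20% trigger as sure to be met because section 3 allows for 20% dropout. That allowance is at one year, the primary endpoint is at five weeks, and the trigger lies above 20%. The SAP gives no expected five-week missingness and does not say at which visit the 20% is judged. Since section 6.2.2 puts all visits in one model, a covariate brought in by late missingness could still alter the five-week estimate.
- Conversion to open surgery is not a usable example. Section 5.3 defines it only for patients allocated to VATS.
- Time of measurement is not the right test. Benign disease is established at or after surgery (section 5.3) but was present before randomisation. It predicts later missingness by design, because the note to Figure F1 says these patients are followed only to five weeks. A rule limited to variables measured before surgery would wrongly bar it.
- For the same covariates under MAR, a likelihood-based mixed model and imputation use essentially the same information, so the remark on imputation is fair within that scope.
- The illustrated bias is simply the product of the assumed inputs and is no evidence about this trial.

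None of this supplies the missing condition or narrows the unbiasedness statement.

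**Conclusion.** The point holds as a defect of wording that can bias the primary analysis if the rule is triggered and used with the wrong kind of variable. The unbiasedness statement is correct for covariates that allocation cannot affect, under MAR. It is wrong for a covariate that allocation changes and that bears on function.

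The size cannot be known from the SAP. Under the assumptions above, the loss is 0.025 to 0.075 SD, or 10% to 30% of the 0.25 SD target. Not adjusting costs less than 0.01 SD in the same scenarios, so the remedy would do more harm than the missing data.

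The direction depends on which arm has more of the variable: the loss shown assumes that VATS lowers complications, and the reverse would inflate the estimate. The illustration uses a single follow-up score, a constant complication effect, and no unmeasured cause shared by complications and function. The SAP's joint model over all visits could give somewhat different figures, but would not remove the problem.

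**What to change.** Three changes to section 6.2.8:

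1. Limit covariates added to the analysis model to variables that allocation cannot affect: baseline variables, or characteristics present before randomisation such as benign disease.
2. Use predictors of missingness that allocation may affect only as auxiliaries in a multiple-imputation model fitted by arm, then fit the unchanged analysis model.
3. Restrict the sentence on unbiasedness and imputation to covariates not affected by allocation, under MAR.

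It would also help to state at which visit, or over which visits, the 20% is judged.

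The cost is a short SAP amendment and, if the trigger is met, an imputation run with the Stata routine that the SAP already names. The downside is a small amount of extra analysis work, including keeping the imputation consistent with the joint modelling of survival planned in section 6.2.2.

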6.2.9 Multiple testing

For quality of life outcomes derived from the QLQ-C30 and QLQ-LC13 questionnaires, multiple testing will be accounted for by applying the false discovery rate method proposed by Benjamini Y and Hochberg Y⁽⁵⁾. This method will be applied within each instrument (e.g. for QLQ-C30 functional scale scores, QLQ-C30 symptom scale scores and QLQ-LC13 scores). No formal adjustment will be made for multiple testing for other outcomes. However as previously described formal statistical comparisons will not be made for outcomes with low event rates and only pre-specified subgroup analyses will be performed. Consideration will be taken in interpretation of results to reflect the number of statistical tests performed and the consistency, magnitude and direction of treatment estimates for different outcomes.

6.3 Safety data

Adverse events (AEs) and serious adverse events (SAEs) occurring in the study period for all patients in the safety population will be tabulated as per **Table T19 and T20**.

Table T19 summarises AEs and SAEs experienced during the period from randomisation to hospital discharge. Such events are captured via the study CRFs.

Table T20 summarises SAEs experienced during the follow-up period from hospital discharge to 12 months post-randomisation.

All events will be coded using MedDRA and reported according to this classification system. The difference in the proportion of patients with any adverse event and with any serious adverse event (according to the standard GCP definition of serious) will be reported with a 95% CI. The outcome of serious events (alive or died following the event) will be described. The difference in proportion of patients experiencing an event (serious or non-serious) in each MedDRA system organ class group (SOC) will also be reported with 95% CIs for each SOC with events in both groups and at least five events in total across the two groups. These estimates will be displayed in a Forest plot (see Figure F9). P-values will not be included.

8. AMENDMENTS TO THE SAP

[figure not shown]
Previous version	Previous date	New version	New date	Brief summary of changes
1.0	04/07/2019	2.0	11/11/2019	
Addition of the outcome upstaging to pN1 at the request of the chief investigator.
 
Updating analysis models section to state risk ratios and risk differences will be presented instead of odds ratios for binary outcomes.
 
Addition to safety data section to state all events will be MedDRA coded and the difference in proportion of patients experiencing an event in each MedDRA system organ class group will be reported.
 
Update to adjustment in models section to remove adjustment for analgesia in pain score models as it was decided analgesia lay on the causal pathway and may therefore lead to biased estimates. Analgesia will be summarised by group instead.

APPENDIX A: SKELETON TABLES AND FIGURES

The following summarises the planned outputs:

Section	Outputs
Section 1 Population	Tables, figures and listings detailing the study population Figure F1 Flow of participants Figure F2 Predicted and actual recruitment Table T1 Protocol deviations Table T2 Details of conversions from VATS to open surgery Table T3 Withdrawals
Section 2 Baseline and intra-operative data	Summary tables of demographic and operative information Table T4 Baseline demographic and clinical characteristics Table T5 Operative details
Section 3 Additional descriptive information	Summary tables of additional descriptive information Figure F3 Pathology flow chart Table T6 Patient blinding at 2 days post-surgery Table T7 Patient blinding at discharge Table T8 Nurse blinding at discharge Table T9 Nurse blinding at 5 weeks Table T10 Nurse blinding at 12 months
Section 4 Primary and secondary outcome data	Summary data and treatment estimates for primary and secondary outcomes Table T11 Primary outcome Figure F4 Primary outcome Table T12 In-hospital secondary outcomes Table T13 Additional secondary outcomes Table T14 Pain scores in the first two days post-surgery Figure F5 In-hospital secondary outcomes Figure F6 Mean ratios of in-hospital analgesia Figure F7 Additional secondary outcomes Table T15 QLQ-C30 global health status/functional scale scores Figure F8 Global health status over time Table T16 QLQ-C30 symptoms scale scores Table T17 QLQ-LC13 Table T18 EQ5D Table T19 Adverse events and serious adverse events in-hospital Table T20 Serious adverse events during follow-up Table T21 Sensitivity analysis of primary outcome excluding patients with benign disease Figure F9 Adverse events in-hospital Figure F10 Subgroup analysis of pain score Figure F11 Sensitivity analysis of survival outcomes adjusting for pathological disease stage Figure F12 Exploratory analysis of in-hospital pain score by of thoracotomy performed Figure F13 Exploratory analysis of QLQ-C30 pain score by type of thoracotomy performed Table T22 Pain scores by number of port sites Table T23 Exploratory analysis comparing pain scores by number of port sites Table T24 Exploratory analysis comparing length of stay by number of port sites

Figure F1 Flow of participants

Notes:

¹ Patients may be ineligible for more than one reason

Benign patients are only followed-up to 5 weeks post-randomisation; allocated to open (n=xx), allocated to VATS (n=xx)

Figure F2 Predicted and actual recruitment

[figure not shown]

Table T1 Protocol deviations

	Randomised to open (n=XX)		Randomised to VATS (n=XX)		Overall (n=XX)	
	n	%	n	%	n	%
Any protocol deviation						
Patient ineligible but treated in the study						
Patient did not undergo lobectomy						
Patient received the opposite intervention to that they were allocated*						

Notes: *only includes patients who underwent a lobectomy

Table T2 Details of conversions from VATS to open surgery

	Randomised to VATS (n=XX)	
	n	%
Converted from VATS to open		
Reason for conversion		
Technical problems		
Equipment malfunction		
Failure to progress		
Poor visualisation		
Anatomical problems		
Absent or thick fissure		
Calcified peri-arterial nodes		
Chest wall invasion		
Diffuse pleural adhesion		
Requirement for sleeve resection		
Oncological problems		
Discovery of N2 tumours		
Invasion of the artery		
Invasion of the parietal pleura		
Margin extension		

Table T3 Withdrawals

	Randomised to open (n=XX)		Randomised to VATS (n=XX)		Overall (n=XX)	
	n	%	n	%	n	%
Any withdrawal						
Timing of withdrawal						
Post-consent pre-randomisation						
Post-randomisation but before surgery						
After surgery						
Reason for withdrawal						
Clinician's advice						
Surgery no longer appropriate						
Patient no longer eligible						
Other						
Patient's decision						
Referral to another centre						

Patient changed their mind about the study

Patient no longer wants surgery

Refused to give reason

Other

Admin/logistical reasons

Surgeon changed

Other

Further details

Withdrawn from follow-up

Notes:

Other reasons will be provided in footnotes

Table T4 Baseline demographic and clinical characteristics

	Randomised to open (n=XX)	Randomised to VATS (n=XX)	Overall (n=XX)
Baseline characteristics			
Age (years)			
Sex	Male		
	Female		
Smoking status (ever smoked)			
Ethnicity	White or Caucasian		
	Black / Black British		
	Mixed / multiple ethnic groups		
	Asian / Asian British		
	Other ethnic group		
Clinical TNM8 stage			
T1a			
T1b			
T1c			
T2a			
T2b			
T3			
N0			
N1			
M0			
Location of primary tumour			
Left upper lobe			

Left lower lobe
Right upper lobe
Right middle lobe
Right lower lobe
Other

Baseline clinical measures

BMI (kg/m²)

ECOG status 0
1
2
3

Haemoglobin (g/dl)

Platelets (x10⁹/l)

White cell count (x10⁹/l)

Neutrophils (x10⁹/l)

Lymphocytes (x10⁹/l)

CRP (Mg/L)

Creatinine (µmol/l)

Urea (µmol/l)

-Lung function

FEV₁ (% predicted)

FVC (% predicted)

DLCO (% predicted)

Medical history

Family history of lung cancer

Respiratory comorbidity

Neurological dysfunction

Diabetes mellitus

Alcoholism

Previous lung surgery

CVAT/TIAs

Cardiovascular comorbidity

Chronic pain syndrome

Deep vein thrombosis

Previously treated malignancy

Neoadjuvant treatment

Pre-operative treatment

Data are presented as median (interquartile range), mean (standard deviation), or n (%).

Table T5 Operative details

	Randomised to open (n=XX)		Randomised to VATS (n=XX)		Overall (n=XX)	
	n	%	n	%	n	%
Operative strategy						
Frozen section biopsy planned						
Biopsy attempted						
Biopsy diagnostic						
Malignancy confirmed						
Resection details						
Benign disease on frozen section						
Open and close (inoperable/extensive malignancy)						
Resection of airway without removal of lung parenchyma						
Pneumonectomy						
Lobectomy/bilobectomy						
Segmentectomy						
Wedge resection						
Lobectomy and segmentectomy						
Lobectomy and wedge resection						
Lobectomy and resection of airway without removal of lung parenchyma						
Benign disease on frozen section and lobectomy						
Benign disease on frozen section and wedge resection						
Operation details						
First operator classification	Consultant surgeon					
	Trainee surgeon					
Prophylactic mini-tracheostomy tube used						
Number of N1 lymph node stations sampled	0					
	1-2					
	3-4					
	5					
Number of N2 lymph node stations sampled	0					
	1-2					
	3-4					
	5-6					
Anterior thoracotomy performed						

Postero-lateral thoracotomy performed

Muscle sparing approach used

Serratus muscle 'spared'

Latissimus muscle 'spared'

Number of ports/incisions used

1
2
3
4

Duration of drain

Intra-operative analgesia

Single-shot paravertebral block

[figure not shown]
Epidural

Paravertebral catheter

Intercostal block

Other analgesia

Figure F3 Pathology flow chart

Notes: details of the resection in patients undergoing an alternative resection will be provided in footnotes

Table T6 Patient blinding at two days post-surgery

Intervention	VATS	Patient's answer, n (%)			Question not asked, n
		Open	Do not know	Total	
VATS					
Open					
Total					

Blinding index (VATS: open) = X.XX (95% confidence interval [CI], X.XX to X.XX): X.XX (95% CI, X.XX to X.XX) (P=X.XX).

Table T7 Patient blinding at discharge

Intervention	VATS	Patient's answer, n (%)			Question not asked, n
		Open	Do not know	Total	
VATS					
Open					
Total					

Blinding index (VATS: open) = X.XX (95% confidence interval [CI], X.XX to X.XX): X.XX (95% CI, X.XX to X.XX) (P=X.XX).

Table T8 Nurse blinding at discharge

Intervention	VATS	Nurse's answer, n (%)			Question not asked, n
		Open	Do not know	Total	
VATS					
Open					
Total					

Blinding index (VATS: open) = X.XX (95% confidence interval [CI], X.XX to X.XX): X.XX (95% CI, X.XX to X.XX) (P=X.XX).

Table T9 Nurse blinding at 5 weeks

Intervention	VATS	Nurse's answer, n (%)			Question not asked, n
		Open	Do not know	Total	
VATS					
Open					
Total					

Blinding index (VATS: open) = X.XX (95% confidence interval [CI], X.XX to X.XX): X.XX (95% CI, X.XX to X.XX) (P=X.XX).

Table T10 Nurse blinding at 12 months

Intervention	VATS	Nurse's answer, n (%)			Question not asked, n
		Open	Do not know	Total	
VATS					
Open					
Total					

Blinding index (VATS: open) = X.XX (95% confidence interval [CI], X.XX to X.XX): X.XX (95% CI, X.XX to X.XX) (P=X.XX).

Table T11 Primary outcome

Outcome		Randomised to open (n=XX)		Randomised to VATS (n=XX)		Effect (95% CI)	p-value
		Mean/Median	SD/IQR	Mean/Median	SD/IQR		
Physical functioning	Baseline						
	2 weeks						
	5 weeks					MD/GMR	
	3 months						
	6 months						
	12 months						
Test for treatment*time interaction							
Overall treatment effect estimate						MD/GMR	

Notes: higher scores indicate higher levels of functioning
Analyses are adjusted for operating surgeon and centre

Figure F4 Primary outcome

[figure not shown]

Table T12 In-hospital secondary outcomes

Outcome	Randomised to open (n=XX)	Randomised to VATS (n=XX)	Effect (95% CI)	p-value
Duration of hospital stay (days)			HR	
Upstaged from cN0 to pN1 disease after procedure			HR	
Upstaged from cN0 to pN2 disease after procedure			RR/RD	
Complete R(0) resection during procedure			RR/RD	
Any in-hospital adverse event			RR/RD	
Any in-hospital serious adverse event			RR/RD	

Values are presented as median (interquartile range), mean (standard deviation), or n (%). Analyses are adjusted for operating surgeon and centre

Table T13 Post-discharge secondary outcomes

Outcome	Randomised to open (n=XX)	Randomised to VATS (n=XX)	Effect (95% CI)	p-value
Received adjuvant treatment			RR/RD	
Time to uptake of adjuvant treatment (months)			HR	
Overall survival (months)			HR	
Disease-free survival (months)			HR	
Prolonged incision pain			RR/RD	

Values are presented as median (interquartile range) or n (%).
Analyses are adjusted for operating surgeon and centre

Table T14 Pain scores in the first two days post-surgery

Outcome	Randomised to open (n=XX)		Randomised to VATS (n=XX)		Effect (95% CI)	p-value
	Mean/Median	SD/IQR	Mean/Median	SD/IQR		
Pain score	Baseline					
	Day 1 post-surgery				MD/GMR	
	Day 2 post-surgery				MD/GMR	
Test for treatment*time interaction						
Overall treatment effect estimate					MD/GMR	

Analyses are adjusted for operating surgeon and centre

Figure F5 In-hospital secondary outcomes

[figure not shown]
[figure not shown]

Figure F6 Mean ratios of in-hospital analgesia

Notes: point estimate is ratio of mean daily dose of each analgesia in each group. 95% CI calculated by using bootstrap estimation with 10,000 replications to estimate the standard error of the mean ratio

Figure F7 Primary outcome and post-discharge secondary outcomes

[figure not shown]

Table T15 QLQ-C30 global health status/functional scale scores

Outcome		Randomised to open (n=XX)		Randomised to VATS (n=XX)		Effect (95% CI)	p-value
		Mean/Median	SD/IQR	Mean/Median	SD/IQR		
Global health status/QoL	Baseline						
	2 weeks					MD/GMR	
	5 weeks					MD/GMR	
	3 months					MD/GMR	
	6 months					MD/GMR	
	12 months					MD/GMR	
Test for treatment*time interaction							
Overall treatment effect estimate						MD/GMR	
Role functioning	Baseline						
	2 weeks					MD/GMR	
	5 weeks					MD/GMR	
	3 months					MD/GMR	
	6 months					MD/GMR	
	12 months					MD/GMR	
Test for treatment*time interaction							
Overall treatment effect estimate						MD/GMR	
Emotional functioning	Baseline						
	2 weeks					MD/GMR	
	5 weeks					MD/GMR	
	3 months					MD/GMR	
	6 months					MD/GMR	
	12 months					MD/GMR	
Test for treatment*time interaction							
Overall treatment effect estimate						MD/GMR	
Cognitive functioning	Baseline						
	2 weeks					MD/GMR	
	5 weeks					MD/GMR	
	3 months					MD/GMR	
	6 months					MD/GMR	
	12 months					MD/GMR	
Test for treatment*time interaction							
Overall treatment effect estimate						MD/GMR	
Baseline							

Social functioning	2 weeks	MD/GMR
	5 weeks	MD/GMR
	3 months	MD/GMR
	6 months	MD/GMR
	12 months	MD/GMR
Test for treatment*time interaction		
Overall treatment effect estimate		

Notes: higher scores indicate higher levels of functioning
Analyses are adjusted for operating surgeon and centre

Figure F8 Global health status over time

[figure not shown]

Table T16 QLQ-C30 symptom scale scores

Outcome		Randomised to open (n=XX)		Randomised to VATS (n=XX)		Effect (95% CI)	p-value
		Mean/Median	SD/IQR	Mean/Median	SD/IQR		
Fatigue	Baseline						
	2 weeks					MD/GMR	
	5 weeks					MD/GMR	
	3 months					MD/GMR	
	6 months					MD/GMR	
	12 months					MD/GMR	
	Test for treatment*time interaction						
Overall treatment effect estimate						MD/GMR	
Nausea and vomiting	Baseline						
	2 weeks					MD/GMR	
	5 weeks					MD/GMR	
	3 months					MD/GMR	
	6 months					MD/GMR	
	12 months					MD/GMR	
	Test for treatment*time interaction						
Overall treatment effect estimate						MD/GMR	
Pain	Baseline						
	2 weeks					MD/GMR	
	5 weeks					MD/GMR	
	3 months					MD/GMR	
	6 months					MD/GMR	
	12 months					MD/GMR	
	Test for treatment*time interaction						
Overall treatment effect estimate						MD/GMR	
Dyspnoea	Baseline						
	2 weeks					MD/GMR	
	5 weeks					MD/GMR	
	3 months					MD/GMR	
	6 months					MD/GMR	
	12 months					MD/GMR	
	Test for treatment*time interaction						
Overall treatment effect estimate						MD/GMR	
Insomnia	Baseline						

	2 weeks	MD/GMR
	5 weeks	MD/GMR
	3 months	MD/GMR
	6 months	MD/GMR
	12 months	MD/GMR
Test for treatment*time interaction		
Overall treatment effect estimate		MD/GMR
Appetite loss	Baseline	
	2 weeks	MD/GMR
	5 weeks	MD/GMR
	3 months	MD/GMR
	6 months	MD/GMR
	12 months	MD/GMR
	Test for treatment*time interaction	
Overall treatment effect estimate		MD/GMR
Constipation	Baseline	
	2 weeks	MD/GMR
	5 weeks	MD/GMR
	3 months	MD/GMR
	6 months	MD/GMR
	12 months	MD/GMR
	Test for treatment*time interaction	
Overall treatment effect estimate		MD/GMR
Diarrhoea	Baseline	
	2 weeks	MD/GMR
	5 weeks	MD/GMR
	3 months	MD/GMR
	6 months	MD/GMR
	12 months	MD/GMR
	Test for treatment*time interaction	
Overall treatment effect estimate		MD/GMR
Financial difficulties	Baseline	
	2 weeks	MD/GMR
	5 weeks	MD/GMR
	3 months	MD/GMR
	6 months	MD/GMR
	12 months	MD/GMR
	Test for treatment*time interaction	

Overall treatment effect estimate [redacted] MD/GMR

Notes: higher scores indicate higher levels of symptoms
Analyses are adjusted for operating surgeon and centre.

Table T17 QLQ-LC13

Outcome	Randomised to open (n=XX)		Randomised to VATS (n=XX)		Effect (95% CI)	p-value
	Mean/Median	SD/IQR	Mean/Median	SD/IQR		
Dyspnoea	Baseline				[redacted]	
	2 weeks				MD/GMR	
	5 weeks				MD/GMR	
	3 months				MD/GMR	
	6 months				MD/GMR	
	12 months				MD/GMR	
	Test for treatment*time interaction					[redacted]
Overall treatment effect estimate					MD/GMR	
Cough	Baseline				[redacted]	
	2 weeks				MD/GMR	
	5 weeks				MD/GMR	
	3 months				MD/GMR	
	6 months				MD/GMR	
	12 months				MD/GMR	
	Test for treatment*time interaction					[redacted]
Overall treatment effect estimate					MD/GMR	
Haemoptysis	Baseline				[redacted]	
	2 weeks				MD/GMR	
	5 weeks				MD/GMR	
	3 months				MD/GMR	
	6 months				MD/GMR	
	12 months				MD/GMR	
	Test for treatment*time interaction					[redacted]
Overall treatment effect estimate					MD/GMR	
Sore mouth	Baseline				[redacted]	
	2 weeks				MD/GMR	
	5 weeks				MD/GMR	
	3 months				MD/GMR	
	6 months				MD/GMR	

	12 months	MD/GMR
Test for treatment*time interaction		
Overall treatment effect estimate		MD/GMR
Dysphagia	Baseline	
	2 weeks	MD/GMR
	5 weeks	MD/GMR
	3 months	MD/GMR
	6 months	MD/GMR
	12 months	MD/GMR
Test for treatment*time interaction		
Overall treatment effect estimate		MD/GMR
Peripheral neuropathy	Baseline	
	2 weeks	MD/GMR
	5 weeks	MD/GMR
	3 months	MD/GMR
	6 months	MD/GMR
	12 months	MD/GMR
Test for treatment*time interaction		
Overall treatment effect estimate		MD/GMR
Alopecia	Baseline	
	2 weeks	MD/GMR
	5 weeks	MD/GMR
	3 months	MD/GMR
	6 months	MD/GMR
	12 months	MD/GMR
Test for treatment*time interaction		
Overall treatment effect estimate		MD/GMR
Pain in chest	Baseline	
	2 weeks	MD/GMR
	5 weeks	MD/GMR
	3 months	MD/GMR
	6 months	MD/GMR
	12 months	MD/GMR
Test for treatment*time interaction		
Overall treatment effect estimate		MD/GMR
Pain in arm or shoulder	Baseline	
	2 weeks	MD/GMR
	5 weeks	MD/GMR

	3 months	MD/GMR
	6 months	MD/GMR
	12 months	MD/GMR
	Test for treatment*time interaction	
	Overall treatment effect estimate	MD/GMR
Pain in other parts	Baseline	
	2 weeks	MD/GMR
	5 weeks	MD/GMR
	3 months	MD/GMR
	6 months	MD/GMR
	12 months	MD/GMR
	Test for treatment*time interaction	
	Overall treatment effect estimate	MD/GMR
Pain medication	Baseline	
	2 weeks	MD/GMR
	5 weeks	MD/GMR
	3 months	MD/GMR
	6 months	MD/GMR
	12 months	MD/GMR
	Test for treatment*time interaction	
	Overall treatment effect estimate	MD/GMR

Notes: higher scores indicate higher levels of symptoms
Analyses are adjusted for operating surgeon and centre

Table T18 EQ5D

Outcome	Randomised to open (n=XX)		Randomised to VATS (n=XX)		Effect (95% CI)	p-value
	Mean/Median	SD/IQR	Mean/Median	SD/IQR		
EQ5D	Baseline					
	2 weeks				MD/GMR	
	5 weeks				MD/GMR	
	3 months				MD/GMR	
	6 months				MD/GMR	
	12 months				MD/GMR	
	Test for treatment*time interaction					
	Overall treatment effect estimate				MD/GMR	

Analyses are adjusted for operating surgeon and centre

Table T19 Adverse events and serious adverse events in-hospital

Event	Randomised to open (n=XX)				Randomised to VATS (n=XX)			
	All events		SAEs		All events		SAEs	
	n	%	n	%	n	%	n	%
SOC 1								
Event 1								
Event 2								
...								
Event N								
SOC 2								
Event 1								
Event 2								
...								
Event N								
...								
SOC N								
Event 1								
Event 2								
...								
Event N								
Any event								

Figure F9 Adverse events in-hospital

[figure not shown]

Table T20 Serious adverse events during follow-up

[figure not shown]
Event	Randomised to open (n=XX)		Randomised to VATS (n=XX)	
	SAEs		SAEs	
	Events/ patients	%	Events/ patients	%
SOC 1				
Event 1				
Event 2				
...				
Event N				
SOC 2				
Event 1				
Event 2				
...				
Event N				
...				
SOC N				
Event 1				
Event 2				
...				
Event N				
Any event				

Table T21 Sensitivity analysis of primary outcome excluding patients with benign disease

Outcome		Randomised to open (n=XX)		Randomised to VATS (n=XX)		Effect (95% CI)	p-value
		Mean/ Median	SD/IQR	Mean/ Median	SD/IQR		
Physical functioning	Baseline					MD/GMR	
	2 weeks						
	5 weeks						
	3 months						
	6 months						
	12 months						
	Test for treatment*time interaction						

Notes: higher scores indicate higher levels of functioning
Analyses are adjusted for operating surgeon and centre

Figure F10 Subgroup analysis of pain score

Notes: p-value is from the test for interaction, p-values for treatment estimates within each subgroup will not be presented.

Figure F11 Sensitivity analyses of survival outcomes adjusting for pathological disease stage

[figure not shown]

Figure F12 Exploratory analyses of in-hospital pain score by type of thoracotomy performed

[figure not shown]

Figure F13 Exploratory analyses of QLQ-C30 pain score by type of thoracotomy performed

[figure not shown]

Table T22 Pain scores by number of port sites

Time point	Randomised to VATS (n=XX)				Randomised to open (n=XX)	
	Single port (n=XX)		Multi-port (n=XX)		Median	IQR
	Median	IQR	Median	IQR		
Baseline						
Day 1						
Day 2						

Analyses are adjusted for operating surgeon and centre

Table T23 Exploratory analysis comparing pain scores by number of port sites

Outcome	Effect size	95% confidence interval	p-value
Pain score in first two days post-surgery			
Single port VATS vs multi port VATS	MD=X.XX	(X.XX, X.XX)	
Single port VATS vs open	MD=X.XX	(X.XX, X.XX)	X.XX
Multi port VATS vs open	MD=X.XX	(X.XX, X.XX)	

Analyses are adjusted for operating surgeon and centre

Table T24 Exploratory analysis comparing length of stay by number of port sites

Outcome	Median	IQR	Effect size	95% confidence interval	p-value
Length of stay					
Single port VATS vs multi port VATS			MD=X.XX	(X.XX, X.XX)	
Single port VATS vs open			MD=X.XX	(X.XX, X.XX)	X.XX
Multi port VATS vs open			MD=X.XX	(X.XX, X.XX)	

Analyses are adjusted for operating surgeon and centre

